In critiques of the PEPAC study, we identified two key limitations of our face-to-face HC intervention design. First, the brief nature of the PEPAC intervention likely constrained the effects on behavior change. In our proposed study, we will extend exposure to intervention content via mobile phone based text-messaging. The rationale for using text-messaging, specifically among this target population, is outlined in the Innovation Section (B.1.b.) below. Second, we did not take into consideration parents' beliefs about their child's asthma. Specifically, as noted in the Social Cognitive Theory,³⁹ in addition to self-efficacy, the parental cognition of outcome expectations, one's beliefs about the costs/benefits of a behavioral choice, may serve as a potentially modifiable factor impacting asthma outcomes. Along with issues of competing priorities, this may play a role in worse asthma outcomes for minority children. Therefore, in the currently proposed intervention, outcome expectations will be targeted by identifying parent's personal goals for their child's asthma outcomes, by sending messages containing relevant asthma information and that reinforce how health communication will help achieve these personal goals. These two key enhancements to the PEPAC intervention will contribute to sustainability of expected health behavior changes.

Innovation

Advantages of mHealth Innovations

mHealth, according to the National Institutes of Health Consensus Group, is defined as the use of mobile and wireless devices to improve health outcomes, healthcare services, and health research.⁴⁴ The efficacy of mHealth technologies (e.g., text-messaging, mobile applications) is in part due to their convenience as a method of health information exchange,⁴⁵ and, similarly, they are effective for modifying health behavior because behavioral cues (e.g., reminders) can be sent/received asynchronously, when and where they are most relevant/appropriate.⁸ Moreover, mHealth technologies are gaining in popularity because they are available at relatively lower cost to payers, providers and patients.⁴⁶

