the primary owners of a mobile phone with text messaging service, which is anticipated to be at least 75% of parents in this population based on previous research on urban, low-income parents.^{59, 60}

Exclusion criteria: Parents of children with significant medical co-morbidities (e.g., sickle cell disease, insulin-dependent diabetes mellitus) will be excluded because of their increased interaction with healthcare providers.

Recruitment and Randomization

CRA's will identify potentially eligible patients through electronic admission board and medical record diagnostic codes after intake into the ED, and they will describe the study to potentially eligible parents while they are waiting to be seen by a provider. Interested families will be screened for eligibility. If eligible, parents will complete the consent process. (See section 5.2.a for more details.) Then the CRA will administer a baseline questionnaire focusing on health care utilization, asthma self-management and morbidity, parental self-efficacy and outcome expectations. After the questionnaire is completed, participants will be randomized to usual care or the intervention group (T2B). Randomization will occur automatically via the RedCap database system. Time allowing, participants randomized to the intervention will receive brief education on the 3 S's and orientation to the text message component (including an "opt-in" code) while in the ED or if necessary by phone within 48 hours. The text message education component will begin within 1 week after participants are randomized, allowing time for participants to enter the opt-in code.

Retention and Compensation

Parents will receive total compensation of \$110 for participation in the study to be dispensed as: \$20 gift card will be given to the parent after he/she completes the baseline interview and \$30 gift cards will be sent after the 3, 6, 12 follow-up interviews; Based on previous studies conducted by our research team with similar populations, this amount should be sufficient to compensate participants for their time and offset the cost incurred for the text messages (if any), but it will not be coercive, minimizing participation solely based on financial gain.

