Trained CRAs will conduct structured in-person interviews after participants have consented and before randomization. Follow-up interviews, lasting approximately 30 minutes, will be conducted by a trained CRA blinded to participants' randomization. In cases when no blinded CRA is available an unblinded CRA may complete the survey. Unblinded status will be documented for each survey conducted. Electronic medical record review will be conducted by trained study staff at the site where the participant was enrolled. Measures of asthma outcomes for this study are aligned with the recent recommendations of the Asthma Outcomes Groups for standardization of definitions and data collection methodologies for asthma research studies and clinical trials.^{75,76} All, but one of the following measures will be administered at each wave of data collection. The Asthma Self-Management Questionnaire will be administered at baseline and 12 months. (see appendix for Baseline Survey).

Distal Outcome Measures – Child Asthma Outcomes

ED visits for asthma care: Parents will report whether and how many times their child was taken to the emergency room because of asthma during the past 12 months using 2 questions administered in several national-scale surveys;⁷⁵ they will also indicate whether those visits included receipt of systemic corticosteroids.⁷⁶ We will validate a large portion of this data with EMR review because Seattle Children's is the primary ED utilized by young patients in the Seattle area and Mary Bridge Children's the primary ED utilized by young patients in the Tacoma area.

Asthma Morbidity: Asthma morbidity will be assessed by the questions used in the Inner City Asthma Consortium (ICAC)^{73, 74, 77, 78} and applied subsequently in numerous studies, including the study validating the IMPACT DC intervention.¹⁵ Morbidity will be measured as the number of days (or nights) of impairment in the prior 2 weeks.

Proximal Outcome Measures – Adherence to Treatment Recommendations

Primary Care Utilization: To maintain continuity in outcomes with the IMPACT DC RCT,¹⁵ we will ask parents to identify their child’s primary asthma health care provider, as well as their child’s primary care provider. A computed variable will indicate whether the named PCP is the child’s primary asthma health care provider. In addition, we will ask parents about frequency of PCP visits for asthma care at each telephone follow-up interview.

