Text messages will be individually tailored to include child and parent initials and, child's gender, Parents will also choose one goal important for improving management of their child's asthma and for communicating with their child's PCP regarding asthma care. A component of their text message communication education content will be based on their identified goal. Information for the tailored messaging will be collected as part of the baseline survey and will be verified and updated at the 3, and 6 month telephone interviews.

Two to three education messages will be sent each week for the first 3 months, one focused on an IMPACT DC asthma education message and a second on a PEPAC health communication message. Parents in our focus groups indicated that this frequency of messages would not be burdensome but welcomed and useful. Parents will also receive text message reminders to follow up with their child's PCP for asthma care at appropriate times based on the asthma care guidelines and relative to the date of the ED visit/enrollment into the program. Parents will also be prompted to reply to the text confirming a scheduled appointment with their child's PCP. Some messages will prompt participants to respond (e.g., key content questions, follow-up reminders for PCP visits, achievement of asthma management goals). Once a participant replies to a text message, the system will send a subsequent text message with appropriate feedback. The program will also allow participants to send a variety of keywords at any time to receive additional messaging. This will allow parents, for example, to request the 3 S's during a visit with the PCP. Other messages may include an embedded link to a URL with additional relevant content (e.g., videos demonstrating proper inhaler technique, explanation of controller vs. rescue inhalers), which we anticipate most participants will be able

to access on their mobile device given the majority of urban, low-income parents in a recent study owned smart phones.⁵⁹

Table 1. Text Message Healthcare Communication and Asthma Education Content

Theoretical Construct	Component of Intervention	Content	Week(s)
Outcome Expectations	Introduction to program	
 Welcome to Text2Breathe. As part of this study we will be sending you messages 2x/week over the next 4 months. (interactive) 	1-2
	Tailoring questions	
 Participant's initials, Child's initials, , Child's gender 	

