	Identification of personal goals (tailored)	
 Fewer ED visits Missing less school Be more active Follow-up with PCP every 3 months 	
Facilitation	Education	
 2-3 messages/week – Personalized, Interactive Examples will be based on stated information and goals (personalized) Statement with response required about correct answer for example given (interactive) Asthma Education Example –Controller medications should be taken every day. Choose a time a day that you and [child's initials] will remember. Txt MEDS 4 info. Health Communication Example –Saying It Back is important 2 b sure you know your child's asthma plan. Txt 3SS for help on what to ask. 	3-12
	Reminder Messages	
 Reminder to follow-up with PCP, Influenza Vaccine Reminder Example –Time 4 [child's initials] 2 follow-up with PCP. Did u make an appt? Reply YES or NO. Reminder to schedule study follow up call 	
Self-efficacy	Keyword requests	
(3SS) –Info from communication toolkit (PCP) – Reminder of when to follow-up with PCP (GOAL) - Reminder of parent's intervention goals
 
(MEDS) – Info on difference between controller and rescue medications (TRIGGERS) – Info on common triggers
	13-52 or On demand

Participants will receive a handout with instructions on how to interact with the text message intervention (including opt-in instructions and numbers to call for problems). In addition, parents will be informed that the text messaging system is automated and their responses will be sent to a secured computer system so they should not send text messages seeking medical care. Should the participant send a text message to the system that does not align with the algorithm response programming, they will receive a standard message with instructions to contact the T2B team, their health care provider or 911 if it is an emergency. Research staff will also have the capacity to monitor participant engagement with the system to

troubleshoot any problems. Participants randomized to T2B, intervention, group will also receive a wallet sized “tool kit” reminding them of the 3 S’s and the key words to request text information.

REFERENCES CITED

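### The parent's chosen goal, a listed T2B component, appears to be collected before randomisation and updated in blinded interviews; this conflicts with Table 1 and may prompt controls or reveal the arm

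*Protocol*

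**What the plan says.** Study Intervention (Protocol) describes tailoring by initials and child's gender, then adds: "Parents will also choose one goal important for improving management of their child's asthma". Part of the communication content is built on that goal. The same paragraph ends by saying that the tailoring information is "collected as part of the baseline survey and will be verified and updated at the 3, and 6 month telephone interviews".

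Recruitment and Randomization fixes the order at enrolment: "After the questionnaire is completed, participants will be randomized to usual care or the intervention group (T2B"). Data Collection says follow-up interviews "will be conducted by a trained CRA blinded to participants' randomization"; an unblinded CRA may step in only when no blinded one is available, and this is documented.

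Two places treat goal-setting as part of the intervention. Lessons Learned from a Face-to-Face HC Intervention says "outcome expectations will be targeted by identifying parent's personal goals for their child's asthma outcomes", together with messages that tie communication to those goals. Table 1 lists "Identification of personal goals (tailored") in its column of intervention components, under Outcome Expectations, in the weeks 1-2 block. Its example goals include fewer ED visits and PCP follow-up every 3 months.

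The only texts described for controls are reminders to schedule with the PCP and to get the flu vaccine.

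**The concern.** A component meant to distinguish the arms should be delivered after randomisation and only in the intervention arm. A goal item in a survey that precedes randomisation reaches everyone. The example goals are not neutral: one names the primary outcome and another the Aim 2 behaviour.

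Updating the goal inside a blinded interview creates a second difficulty, because only one arm has a use for the answer. The interviewer either asks everyone, and so prompts controls about goals again, or asks T2B parents only, and so learns the arm.

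At stake are the T2B contrast on outcome expectations (an Aim 3 outcome and hypothesised mediator) and the blinding of interviews that yield mainly parent-reported data. SAP C.5.b uses data from each follow-up in path models and in latent growth models, so the 3- and 6-month interviews matter even though month 12 is the primary time point.

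**Working it through.** **1. The plan's own figure.** SAP C.5.c takes 110 analysable per group and 80% retention: 110 / 0.80 = 137.5, rounded up to 138 per group, or 276 in total. This reproduces. The point itself rests on no sample-size figure.

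**2. The passages side by side.**

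| Place | What it implies for the goal |
|---|---|
| Study Intervention, tailoring paragraph | In the baseline survey; updated at months 3 and 6 |
| Recruitment and Randomization | Survey comes before allocation; its listed topics do not mention goals |
| Table 1 | T2B component, weeks 1-2 of the text programme, in a row separate from the tailoring questions |
| Data Collection | Months 3 and 6 are conducted by a CRA blinded by default |

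The goal sentences stand directly before the sentence on where tailoring information is collected, so the natural reading includes the goal. Table 1 points to a time after randomisation. The baseline survey itself is in an appendix not available here, so the conflict cannot be settled from the text.

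**3. Baseline, if Study Intervention is followed.** No arm exists yet, so the item cannot be limited to T2B. All 276 parents choose a goal, 138 of them controls.

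**4. Months 3 and 6, if Study Intervention is followed.**
- Everyone is asked: blinding is kept, but each control is prompted up to twice more.
- Only T2B parents are asked: up to 138 x 2 = 276 interviews, before attrition, carry a question that reveals the arm.

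The documents do not assign the update to other staff, place it after the outcome questions, or say whether controls are asked.

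**5. How much dilution would matter.** The documents give no effect for choosing a goal. The figures below show what would be needed to matter, not what to expect.

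- *Aim 3, 0.5 SD.* With 110 per group, the smallest effect with 80% power is (1.960 + 0.842) x sqrt(2/110) = 0.378 SD. The planned effect would have to shrink by 0.122 SD, or 24%, to reach that.
- *ED visits.* Power = Phi(|ln IRR| x sqrt(110/V) - 1.960), with V = 1/r0 + 1/r1 + 2k, r0 = 1.28 and r1 = 1.28 x 0.65 = 0.832. The SAP gives no dispersion k; k = 0.11 is assumed because it makes 125 per group yield 90% power. With r1 held fixed:

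| Assumed fall in control rate | IRR | Power, 110 per group |
|---|---|---|
| 0% | 0.65 | 86% |
| 2.5% | 0.667 | 81% |
| 5% | 0.684 | 76% |
| 10% | 0.722 | 62% |

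Nothing in the documents says where in this range, if anywhere, the truth lies.

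**The case against.** The strongest reply is that Table 1 shows the intent: goals are chosen by text, after randomisation, in T2B only, and the Study Intervention sentence is loose wording about initials and gender. This is possible and lowers confidence. It does not remove the need to reconcile the passages, because site staff following Study Intervention would put the goal in the survey and the interviews.

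A reader might infer that controls receive the goal-setting component. The documents do not support that. The stated mechanism also needs goal-based messages, and none are described for controls. At most controls choose a goal and are asked about it again, on top of survey questions about ED visits, PCP visits and expectations that they answer anyway.

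A reader might also infer that blinding is necessarily broken at months 3 and 6. It is not: asking all parents preserves it. The two harms are alternatives, and bias within an interview also requires the goal item to come before the outcome questions, an order the documents do not give.

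Nor does the text show that the 6-month update is pointless once scheduled education has ended. The tailoring information includes initials, the reminder example in Table 1 uses the child's initials, and Study Schedule keeps reminders running for 12 months.

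Finally, a large portion of the ED visit data is to be checked against medical records, and no goal update falls at month 12. Both points stand. They limit the bias, though a CRA unblinded earlier may conduct the month-12 interview, and record checks do not address dilution.

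**Conclusion.** The point holds as a conflict between passages with a real but unsized consequence. If the Study Intervention wording is followed, 138 controls are partially exposed to goal-setting at baseline, and at months 3 and 6 the blinded CRA must either prompt controls again or ask a question that reveals the arm in up to 276 T2B interviews.

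No dilution or bias can be calculated from the documents, and no share of the T2B effect should be attributed to goal choice. Interviewer knowledge matters most for parent-reported outcomes and for the mediation and growth models that use the 3- and 6-month data. It matters less for ED visits and for the 12-month comparison.

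The conclusion assumes that the tailoring information includes the goal, which is the natural reading but not the only one. The point is worth correcting because the correction is cheap.

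**What to change.** Reconcile Study Intervention with Table 1, as follows.

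- Collect the goal after randomisation, in T2B only, at the T2B orientation (in the ED or by phone within 48 hours), with the weeks 1-2 text exchange as back-up.
- Take goal verification and updating out of the 3- and 6-month outcome interviews and let the automated text system do it.
- Leave initials and child's gender in the baseline survey. Updates to initials or contact details can be asked of all parents, which reveals nothing about the arm.

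The cost is protocol wording and a small change to the text programming. Sample size and staffing do not change. The downside is that some T2B parents may not answer the goal text and would receive default content, a realistic prospect where phone numbers change often. Collecting the goal at orientation first limits this.

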COVER PAGE

Text2Breathe: Enhance Parent Communication to Reduce Pediatric Asthma Disparities (T2B)

NCT03032159

July 10, 2014

C.5. Statistical Analyses

C.5.a: Preliminary Descriptive Analysis of Data

We will summarize all baseline variables overall and by study arm to assess the balance achieved by randomization and to check assumptions such as normality and equality of variances. The distributions of continuous variables will be summarized using means, standard deviations, medians, and ranges. Categorical variables will be summarized using frequency distributions. Non-parametric tests (e.g., Wilcoxon rank-sum and Fisher's exact) will be used in subsequent analyses as needed. Cronbach alpha reliabilities will be estimated for 12 all standardized instruments to assess whether the instruments are as reliable in our target population as in the population on which the instruments were validated. Frequency of missing data for each outcome variable will be determined at each time point. Baseline characteristics of missing and non-missing respondents at the 3, 6, 12 and 24 month time points will be compared to assess for attrition bias. We will employ multiple imputation to account for missing data, if necessary.^{84, 85} We will examine counts of mobile interactions captured by Rip Road (e.g., number of messages received and sent by each participant; See section 5.1.d.) to assess engagement with the intervention, overall and by participant characteristics.

C.5.b: Analysis Plan for Addressing Specific Aims

In **Aim 1**, to assess the intervention effect on the primary and secondary distal outcomes (i.e., the number of ED visits for asthma care during the 12-month interval following randomization, and the number of days of impairment during the two weeks prior to the 12-month interview, respectively), we will utilize negative binomial regression, a generalization of Poisson regression which yields unbiased inference even if the outcome variable is over-dispersed (i.e., the variance exceeds the mean) to estimate incidence rate ratios (IRRs) and 95% confidence intervals (CIs) for count data. The single independent variable in each model will be study group, and the exponentiated form of its regression coefficient will reflect the relative difference between groups in the annual rate of ED visits or frequency of impaired days.

In **Aim 2**, we will implement a negative binomial regression model to estimate the IRR and 95% CI for number of follow-up visits with the PCP for asthma care over 12 months in the intervention group compared to the usual care group. In addition to the group variable, the model will include a covariate to account for PCP visit frequency prior to randomization. The exponentiated form of the coefficient of the group term will reflect the relative difference between groups in annual rate of PCP follow-up visits for asthma care. We will use linear regression models to examine the intervention effect on knowledge of self-management (continuous scale score). The model independent variables will include study group and pre-randomization level of knowledge of self-management. The magnitude of the group coefficient will provide an estimate of the size and direction of difference between groups controlling for differences in pre-randomization levels.

We will also assess whether primary care utilization (annual rate of follow-up visits) and increased knowledge of self-management mediate the relationship between the assigned communication intervention and child asthma outcomes (defined as frequency of ED and urgent care visits for asthma care and days of impairment). To do so, we will use path analysis models at baseline and each follow-up time separately. To test these hypotheses using longitudinal data, growth trajectories of each outcome will be modeled using multi-process latent growth models (LGM) of these

proximal and distal outcomes. The hypothesized mediating effects of the proximal outcomes will be tested by relating the intervention condition, the latent slope growth factors of the multiple growth processes, and the distal outcomes.⁸⁶

In **Aim 3**, we will use linear regression models, as above, to evaluate the intervention effect on measures of self-efficacy and outcome expectations. We will then use path analysis to assess whether parental self-efficacy and outcome expectations (defined using the three validated instruments) mediate intervention effects on PCP follow-up rates and knowledge of self-management. Although the data collected at the 12-month time point will be used as our primary indicator of intervention effectiveness, we will also utilize data collected through the full 24-month follow-up period to evaluate sustainability of the hypothesized effects of the intervention in the same series of analyses. The above analyses estimate the impact of the intervention at observed levels of acceptance of the intervention and thus estimate the expected average effectiveness of the intervention if implemented in a similar population. We will also estimate the magnitude of the effect on each outcome under alternative levels of engagement in the intervention to provide a range of estimated effects based on greater and lesser levels of engagement. Moreover, we will examine potential moderating effects of race/ethnicity on the intervention effects.

C.5.c: Sample Size Estimate

All sample size and power analyses are based on a 2-tailed type 1 error of 5% in final analyses based on 12 month follow-up results. For the primary outcome under **Aim 1** (number of ED visits for asthma care during a 12-month interval), we calculated that a sample size of 125 per study group provides at least 90% power to detect a clinically important 35% reduction in the T2B group compared to the estimated average rate of 1.28 ED visits per year in the usual care group (based on 2012 ED records). For the primary outcome under **Aim 2** (number of PCP visits for asthma care during a 12-month interval), we calculated that a sample size of 120 participants per group provides 90% power to detect an increase to the recommended 3 annual visits in the T2B group over the observed rate of 1.8/year in the previous IMPACT DC sample.⁷ For the other outcomes under Aim 3 (self-efficacy and outcome expectation), a sample size of 85 per group provides 90% power to detect a 0.5 SD effect size difference between study groups. A feasible **analytic sample size of 110** ensures >80% power in all aforementioned analyses.

In prior studies, we have been able to maintain a 90% retention rate over a 6-month follow-up period. We will employ retention strategies that have been successful in this population in previous studies. Conservatively estimating a retention rate of 80% at the 12-month assessment, we must enroll 138 participants in each group (total N=276). The Seattle Children's ED currently serves approximately 1400 2-12 year old asthma patients per year, 40% (n=530) of whom are Medicaid insured. We estimate that 70% of this total will meet the remaining eligibility criteria (n=371). If 40% of these patients consent to the trial, which is much less than the 60-70% participation rates for Seattle Children's ED-based studies, we will yield our projected sample size of 276 in the proposed 24 month enrollment period. Thus, we estimate that we will need to approach 5-7 parents to recruit at least 3 participants per week, with an estimated recruitment of approximately 12 participants per month (minimum of 6 and maximum of 18 in any given month to assure there is not seasonal over-representation in the study sample).
